10.2.2 Study day for Safety Measures and Efficacy

If the date of interest occurs on or after the safety or efficacy reference date, then the study day will be calculated as:

Study day = (date of interest – reference date) + 1

There is no safety or efficacy study day 0

10.2.3 Duration and Elapsed Time

Durations (e.g. duration of an adverse event, duration of exposure, etc.) are calculated as:

Duration = (Stop date - Start date) + 1

Elapse times (e.g. time since initial diagnosis) are calculated as:

- Reference date is on or after the event date = (reference date event date) + 1
- Reference date is before the event date = reference date event date

10.2.4 Creatinine Clearance (CrCl)

Cockcroft-Gault equation to calculate creatinine clearance (CrCl):

(140-age[yrs])*weight [kg]* (Z)	Z = 1.0, if Male
Cr (mg/dL) * 72	Z = 0.85, if Female

10.2.5 Baseline Definition

Baseline or pre-dose assessment is defined as the most recent, non-missing available assessment prior to time of first dose, unless is specified otherwise. If there are multiple assessments collected on the same scheduled time, the average of these assessments will be used. For tabulated safety summaries, only the schedule assessments will be included in the summary tables.

10.2.6 Change from Baseline

The change from baseline will be calculated by subtracting the baseline values from the individual post-enrollment values. If either the baseline or the post-enrollment value is missing, the change from baseline is set to missing as well.

10.2.7 Pharmacokinetic Parameters

Plasma pharmacokinetic parameters will be summarized and analyzed after undergoing logtransformation (except tmax).

10.3 Assessment Windows

Actual dosing and PK sampling times will be used in the calculation of the PK parameters. Nominal times will be used for purposes of summarization.

EOT assessments should be performed on the calendar day of, or within 2 days following the last dose of any test article. If a subject withdraws prematurely or terminates participation in the study prior to completion of the planned antibiotic therapy, the EOT visit should be conducted on that day.

The PTE assessment is to be performed 5 to 10 days after the subject's last day of therapy.

The final follow up (FFU) assessment should be conducted within 30-37 days following the subject's first dose of test article.

For each safety outcome, analyses will utilize assessments occurring during the scheduled visit windows (provided below). Thus, if a subject has a visit outside the scheduled visit window, for example, a PTE Visit occurred 20 days after the subject's last day of therapy, the assessment will not be summarized with the PTE Visit but will be considered an unscheduled assessment. If a subject does not have an assessment at a scheduled visit and an unscheduled assessment was taken within the window for the time point (for example, 5 to 10 days after the subject's last day of therapy for PTE), these assessments will be summarized in the by time point analyses. If more than one measurement is taken during the visit window, the value taken on the scheduled visit will be utilized or if no scheduled visit was done, the first (earliest) measurement in the visit window will be used. If more than one measurement is taken on the same day, the assessment closest to the start of the dose will be used for on treatment values.

For worst overall post-baseline analyses, all assessments including those obtained from unscheduled visits will be included.

Scheduled Study Visits

Study Visit	Study Day	Notes
Baseline	Day -1 or Day 1	Except where indicated, last measurement prior to the first dose of test article. Screening assessments are to be taken within 24 hours prior to the first dose of test article. If no test article is taken, the date and time of enrollment is used in place of the first dose of test article.
On Treatment	Day 1-Day 10	A Day 10 visit will be conducted for subjects with treatment extending beyond 9 days, unless this visit coincides with the EOT Visit.
EOT		Within 2 days following the last dose of test article
PTE		5-10 days after the subject's last day of therapy
Final Follow-up	Day 30-37	30-37 days after the start of the first dose of test article

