8.5 Vital Signs

Vital signs include blood pressure (BP), heart rate, pulse oximetry, RR, and body temperature.

• Blood pressure and heart rate should be measured within 30 min before, and approximately (± 15 minutes) 1 hour after the completion of the first dose.

The subject's BP and heart rate should be captured after at least 5 minutes (+ 5 minutes) of rest while in a non-standing position (supine or semi-recumbent, head of bed from 0° to 90°). Subsequent vital sign measurements should be captured in the same non-standing position.

Systolic and diastolic BP will be measured using an automated calibrated device, with an appropriately sized cuff.

A pulse oximeter should be used to capture oxygen saturation.

Heart rate will be measured using an automated calibrated device, when available. If not available, heart rate will be measured manually.

Temperature will be obtained using an electronic (rapid reading) device whenever possible.

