12.6 Secondary Endpoint(s)

12.6.1 Safety Endpoint(s)

All safety analyses will utilize the Safety population. Summary tables will be provided for all treatment-emergent adverse events (TEAEs). A TEAE is defined as an AE with a start date and time on or after the first dose of test article. Adverse events will be coded using the Medical Dictionary for Regulatory Activities (MedDRA) and will be summarized by presenting the number and percentage of subjects having each TEAE by system organ class (SOC) and preferred term (PT), by SOC, PT and severity, and by SOC, PT and relationship to test article. Additional tabulations will provide summarise by SOC and PT of subjects experiencing SAEs and TEAEs leading to discontinuation of test article. Treatment-emergent adverse events leading to dose interruption of test article, and TEAEs of special interest.

The following variables will be analyzed descriptively in the Safety population:

- Vital signs (systolic and diastolic BP, pulse/heart rate, body temperature, pulse oximetry, RR), including change from Baseline by time point measured
- Clinically notable vital signs (meeting predefined criteria as specified in the SAP) by time point measured
- Laboratory parameters, including change from Baseline by visit and overall worst post-baseline
- Clinically notable laboratory parameters (meeting predefined criteria as specified in the SAP) by visit and overall worst post-baseline

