- ^m A full physical examination will be completed at Screening, thereafter only changes from Screening measurements should be recorded as AEs in the eCRFs.
- ⁿ Vital signs include body temperature, BP, pulse oximetry, pulse/heart rate, and RR.
- ^o BP and heart rate should be measured within 30 min before, and approximately (± 15 minutes) 1-hour after the completion of the doses on Day 1.
- PK sample collection on Day 1:within an hour prior to Dose 1, 1, 1.5, 2, 2.5, 3, 4, 6, 8, 12 hours (12 hour taken immediately before Dose 2); Dose 2 administered (times relative to Dose 1); 13, 13.5, 14, 14.5, 15, 16, 24 hours post dose
- ^q PK sample collection on Day 2:within an hour prior to dose, 1, 1.5, 2, 2.5, 3, 4, 6 hours ^r PK sample collection on Day 3: prior to the Day 3 dose
- ^s PK sample collection on EOT is anytime during the visit after the final dose.

Study Phase Screening ^a	Treatment Phase	Follow-up Phase
------------------------------------	-----------------	-----------------

t

The total duration of test article therapy for all subjects will be 7 to 10 days, up to 14 days for bacteremia. A subject's AEs and SAEs will be recorded and reported from signing of the ICF to the Final Follow-up assessment. u

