3 STUDY DESIGN

This is an open-label Phase 1b study evaluating oral omadacycline in the treatment of adults with CABP.

This study is intended to evaluate the PK of an oral dosing regimen in adults with CABP. Subjects will initiate treatment with an oral loading dose of 300 mg BID on Day 1 followed by 300 mg on subsequent days.

Following a screening period of up to 24 hours, eligible subjects will be assigned to receive 7 to 10 days of po treatment. Subjects with baseline bacteremia (i.e., confirmed from local blood culture drawn at screening) can receive up to 14 days of treatment after consultation with the medical monitor.

Subjects may receive oral treatment in either inpatient or outpatient settings, provided that all assessments can be completed at the timepoints required by protocol.

Test Article	Study Day	Study Day	Study Days
	1	2	3-10
Omadacycline	300 mg po BID	300 mg po QC	300 mg po QC

Eligible subjects will be assigned to the following treatment groups.

po = per oral, a dosing day is a 24-hour day not a calendar day

a The total duration of treatment is 7 to 10 days. Treatment duration can be extended to up to 14 days for subjects with bacteremia that, in the opinion of the investigator, requires more than 10 days of treatment.

Refer to the Schedule of Events (Appendix 1) for the summary of subject visits and assessments through end of treatment (EOT).

Subjects will return to the study site for a Post Therapy Evaluation (PTE) 5 to 10 days after the last dose of test article. A Final Follow-up visit (FFU) will be conducted within 30 to 37 days following the first dose of test article. The FFU assessment may be conducted via telephone contact or by another interactive technology for subjects who had an outcome of Clinical Success in the opinion of the investigator at EOT and PTE and had no AEs or clinically significant laboratory or electrocardiogram (ECG) abnormalities noted at or after the PTE visit. Otherwise, this assessment is to be performed with an in-person study visit.

Subjects will participate in the study for up to 37 days. Following a screening period of up to 24 hours, eligible subjects will be assigned to receive treatment. Eligible subjects will be assigned to receive 7 to 10 days of po treatment. Subjects with baseline bacteremia (i.e., confirmed from local blood culture drawn at screening) can receive up to 14 days of treatment after consultation with the medical monitor.

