8.2 Vital Signs

Vital signs include blood pressure (BP), heart rate, pulse oximetry, RR, and body temperature.

Descriptive statistics of the change from baseline to each post-baseline time point and the highest and lowest post-baseline value will also be provided. Baseline is defined as the value closest to but prior to the initiation of test article administration.

Post-baseline vital signs will be defined as clinically notable (CN) if they meet the criterion value or both the criterion value and the change from baseline criterion listed in Appendix 4. The incidence of CN vital signs will be summarized by time point and will be listed and flagged in by-subject listings. The overall post-baseline incidence of CN values for each vital sign parameter, which includes values from unscheduled post-baseline visits, will also be summarized. A listing will also be provided of subjects with a CN vital sign and will list all values for a vital sign noted as CN.

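### On Day 1 the SAP's one-value-per-day rule can displace scheduled 1-hour post-dose blood pressure and heart rate readings from the by-time-point safety tables

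*SAP*

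**What the plan says.** SAP 10.3 sets the windows for safety summaries. Its on-treatment window runs from Day 1 to Day 10, and its visit table has no pre-dose or post-dose slots within a day. When a day has several measurements, "the assessment closest to the start of the dose will be used for on treatment values".

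Two places schedule the Day 1 readings. Protocol 8.5 wants blood pressure and heart rate "measured within 30 min before, and approximately (± 15 minutes) 1 hour after the completion of the first dose". Footnote o of the schedule of events, printed in the protocol and again in SAP Appendix 1, gives the same windows but ends "1-hour after the completion of the doses on Day 1". Day 1 has two doses: "Subjects will initiate treatment with an oral loading dose of 300 mg BID on Day 1".

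On baseline, SAP 8.2 states: "Baseline is defined as the value closest to but prior to the initiation of test article administration". It then promises changes from baseline at each later time point and clinically notable incidence by time point. Protocol 12.6.1 lists as a safety variable: "Clinically notable vital signs (meeting predefined criteria as specified in the SAP) by time point measured".

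**The concern.** The 1-hour readings are the only vital signs scheduled for a set interval after a dose, so they are the ones placed to show an acute effect on blood pressure or heart rate. Safety is the secondary objective, and the plan promises these variables by time point.

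The same-day rule works on the calendar of the day and the clock distance to the dose. A reading taken just before a dose is nearer to it than one taken an hour later. Applied to Day 1 as written, the rule would fill the Day 1 row with a value that cannot show a response to the dose just given. Two programmers following the same text could also put different readings in that row and produce different tables.

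**Working it through.** The plan states no figure here to reproduce. The check applies the rule to the scheduled windows.

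**Inputs**
- Pre-dose window: 0 to 30 min before the dose (Protocol 8.5; footnote o).
- Post-dose window: 60 ± 15 = 45 to 75 min after the dose is completed (same sources). The rule measures from the start of the dose, so the distance is at least 45 min.
- Dose 2 at 12 h = 720 min after Dose 1. This is an assumption, taken from the PK schedule in SAP 7.1, where the 12-hour sample immediately precedes Dose 2.

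**Step 1. Distance of each reading from each dose (minutes)**

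| Reading | From Dose 1 | From Dose 2 |
|---|---|---|
| Before Dose 1 | 0–30 | 720–750 |
| 1 h after Dose 1 | 45–75 | 645–675 |
| Before Dose 2 | 690–720 | 0–30 |
| 1 h after Dose 2 | 765–795 | 45–75 |

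**Step 2. Compare.** The farthest in-window pre-dose reading is 30 min from its own dose and the nearest post-dose reading is 45 min. The gap is at least 45 − 30 = 15 min, so a pre-dose reading always beats the 1-hour reading for the same dose if both are eligible.

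**Step 3. Apply the rule under each reading of the text.** Stepping through the windows in 5-minute steps gives the outcome shown in every combination.

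| Readings taken | Pre-Dose 1 value eligible? | Reference dose | Value selected | 1-hour readings lost |
|---|---|---|---|---|
| Dose 1 only (Protocol 8.5) | Yes | Dose 1 | Before Dose 1 | 1 of 1 |
| Dose 1 only (Protocol 8.5) | No | Dose 1 | 1 h after Dose 1 | 0 of 1 |
| Both doses (footnote o) | Yes | Dose 1 | Before Dose 1 | 2 of 2 |
| Both doses (footnote o) | Yes | Either | Before Dose 1 or before Dose 2 | 2 of 2 |
| Both doses (footnote o) | No | Dose 1 | 1 h after Dose 1 | 1 of 2 |
| Both doses (footnote o) | No | Either | Before Dose 2 | 2 of 2 |

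Footnote o implies up to 2 × 2 = 4 readings on Day 1, of which the rule keeps one. The loss is therefore 1 or 2 of the two 1-hour readings in every footnote o row.

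**Step 4. Consequence for change from baseline.** Where the pre-Dose 1 reading is selected, it is also the baseline under SAP 8.2, so the tabulated change is baseline − baseline = 0 by construction. This applies only where that reading is eligible.

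**Step 5. Where the readings survive.** SAP 5 lists all collected data. SAP 8.2 flags clinically notable vital signs by subject, summarises the highest and lowest values after baseline, and gives overall notable incidence. SAP 10.3 keeps every assessment for worst-value analyses.

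**The case against.** The best answer is that the baseline reading is not an on-treatment value. The rule is limited to on-treatment values, the SAP 10.3 visit table gives baseline a separate row, and SAP 8.2 tabulates changes at time points after baseline. With the pre-Dose 1 reading set aside, Protocol 8.5 leaves a single Day 1 reading, the 1-hour one, and the rule selects it. This is a sound reading, and it rules out any claim that a pre-dose value is chosen in all cases. But SAP 10.3 does not state the exclusion. SAP 10.2.6 defines change using values after enrolment, and Protocol 7.5.1 puts the first dose on the morning after enrolment, so the pre-Dose 1 reading can itself count as one of those values. Under footnote o, the exclusion still leaves at least one 1-hour reading untabulated.

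A second answer is that the pre-dose and 1-hour readings are separate time points and the same-day sentence only settles duplicates. SAP 10.2.5 does refer to scheduled times, and on this reading nothing is lost. The text does not secure it: the rule is keyed to the day, SAP 10.3 uses the term time point for visit windows, and its sentence on nominal times follows one about PK sampling. The intention to report by time point is clear; the rule as worded works against it.

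A reader might infer something stronger: that the rule always picks a pre-dose value, that every subject's Day 1 change is zero with no spread, or that the post-dose readings vanish from the analysis. The documents do not support this. The first two need the baseline reading to count as its own post-baseline value, or footnote o together with either dose as reference. The third is contradicted by the listings and overall summaries.

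**Conclusion.** SAP 10.3 is ambiguous for Day 1 blood pressure and heart rate and, read literally, selects a pre-dose reading over the 1-hour reading. Under the schedule the SAP itself prints, every same-day application drops one or both 1-hour readings from the by-time-point change and clinically notable tables. Under Protocol 8.5 the single 1-hour reading is lost or kept depending on whether the baseline reading is eligible.

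The effect is confined to Day 1 blood pressure and heart rate in those tables. They are descriptive displays in an open-label, single-arm study of up to 30 subjects; no decision rule rests on them and the primary PK analysis is untouched. It should still be corrected, because a stated rule can displace scheduled safety readings from tables the plan promises.

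This rests on readings taken within their windows and Dose 2 at about 12 h. An out-of-window reading could change which value is selected for a subject.

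**What to change.** In SAP 10.3:
- Treat each scheduled Day 1 pre-dose and 1-hour post-dose blood pressure and heart rate reading as a separate nominal time point.
- Apply the closeness rule only to repeats within one nominal time point.
- State that the baseline reading cannot be selected as a post-baseline value.

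Separately, Protocol 8.5 (readings around the first dose) and footnote o in both schedules (readings around the Day 1 doses) must be reconciled so that all sites collect the same data. The table rows should follow whichever schedule results.

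The cost is a few sentences in the SAP, a few extra table rows and one protocol clarification. The SAP change needs no new assessments or design change, since it tabulates readings that are already scheduled.

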10.4 Clinically Notable Values

- Clinically notable laboratory parameters, meeting predefined criteria as values with 2 grade increases will be listed
- Clinically notable vital signs, meeting predefined criteria as specified in Appendix 4 by time point measured

11 OTHER RELEVANT DATA ANALYSES/SUMMARIES

11.1 Prior and Concomitant Medications

All medications taken within 7 days prior to the date of informed consent through the Final Follow-up Visit will be recorded on the eCRF. Prior medications will be summarized by WHODRUG (Version 01 Dec 2014) Anatomical Therapeutic Chemical Classification (ATC) level 3 (third level indicates the therapeutic/pharmacologic subgroup) and generic medication name. Medications are considered prior if taken prior to the first dose of test article or if their start date is unknown. Subjects will be counted only once for an ATC class and generic medication name. Concomitant medications taken during and after the study treatment period will be similarly summarized. Medications are considered concomitant if taken on or after the first dose of test article, or if their stop date is unknown or marked as continuing.

The number and percentage of subjects who receive the following prior and concomitant medications will be summarized:

• Systemic antibacterial medications taken within 72 hours prior to first dose of test article and the reasons for receipt (ITT)

11.2 Resource Utilization Analyses

The number of subjects who are in-patient at the start of the treatment and how many days were spent in hospital will be summarized.

12 CHANGES FROM THE PROTOCOL

In the protocol, the PK Analysis Set was defined to include subjects who receive omadacycline and have PK samples collected. If any subject has an emesis within 2.5 x median T_{max} after dosing, the subject may be excluded from PK Analysis Set. In the SAP, the PK Analysis Set has been defined to include subjects who receive study drug and have at least 1 evaluable PK parameter. If any subject has an emesis within 4 hours after dosing, the subject will be excluded from PK Analysis Set.

Any changes from this statistical analysis plan will be documented in the CSR for this study.

Appendix 4 Criteria for Clinically Notable Vital Signs

Appendix 1 Schedule of Events

Study Phase	Screening ^a	Tr	eatmei	Follow-up Phase			
Study Day ^b		Day 1	Day 2	Day 3	Day 7- 10/ EOT ^c	PTE ^d	Final Follow-up ^e
Signed Informed Consent ^f	Х						
Medical History, current medical	v						
conditions, demography	А						
Assessment of CABP symptom	v		v	v	v	v	
severity ^g	Λ		Λ	Λ	Λ	Λ	
Chest X-ray or CT scan ^h	Х						
PORT Risk Class, ABG (or pulse oximetry) ⁱ	Х						
Blood samples for local lab hematology/chemistry//pregnancy test ^j	Х				Х	Х	
Urine samples for local lab urine tests/pregnancy test ^j	Х						
Review of Inclusion and Exclusion criteria/Treatment Group Assignment (if Eligible)	Х						
Test Article Administration and Accountability ¹		Х	Х	Х	Х		
Physical examination ^m	Х		Х	Х	Х	X	
Vital signs ⁿ							
Height and weight	Х						
Body temperature	Х	Х	Х	Х	Х	Х	
Blood Pressure	Х	Xo	Х	Х	Х	Х	
Pulse Oximetry	Х	Х	Х	Х	Х	Х	
Pulse/Heart Rate	Х	X°	Х	Х	Х	Х	
Respiratory Rate	Х	Х	Х	Х	Х	Х	
Plasma samples (in heparin) for PK analyses		X ^p	Xq	Xr	X ^s		
Assessment for need for continued therapy ^t		X X					
Investigator's Assessment of Clinical Response					Х	Х	
Adverse Events ^u	X X						
Prior/Concomitant Medications and Procedures ^k	X						
A					Λ		
Utilization	Х				X		

ABG = arterial blood gas, AE = adverse event, BP = blood pressure, β -hCG = beta – human Chorionic Gonadotropin, CABP = community-acquired bacterial pneumonia, CT = computed tomography, CXR = chest X-ray, eCRF = electronic case report form, EOT = end of treatment, ICF = informed consent form, IxRS = Interactive Voice Response System/Interactive Web Response System, PK = pharmacokinetics, PORT = Pneumonia Outcomes Research Team, PTE = post-therapy evaluation, RR = respiratory rate, SAE = serious adverse event.

- ^a Following the signing of an ICF, all Screening evaluations, with the exception of the radiographic confirmation of pneumonia, should be completed within the 24 hours prior to treatment group assignment. The radiographic confirmation of pneumonia should be completed within the 48 hours prior to the first dose of test article.
- ^b Study Day 1 is the first day of test article administration. Subsequent study visit days may be consecutive calendar days.
- ^c To be conducted on the day of, or within 2 days following the last dose of test article. Should also be conducted for any prematurely withdrawn subject.
- ^d To be conducted 5 to 10 days after the subject's last day of therapy.
- ^e To be conducted 30 to 37 days after the start of the first dose of test article. The Final Follow-up assessment may be conducted via telephone contact or by another interactive technology for subjects who were considered to be Clinical Successes and had no AEs or clinically significant laboratory, or ECG abnormalities noted at or after the PTE visit. Otherwise, the visit must be conducted in person.
- ^f Written and signed ICF must be obtained before any assessment is performed.
- ^g The investigator should assess the severity of the subject's CABP symptoms of cough, sputum production, pleuritic chest pain, and dyspnea based upon the Community Acquired Bacterial Pneumonia Subject Symptom Severity Guidance Framework for Investigator Assessment (Appendix 3).
- ^h Subjects must have a confirming CXR or CT scan consistent with acute bacterial pneumonia within the 48 hours prior to the first dose of test article.
- ⁱ Only subjects with a PORT Risk Class of II or III for whom oral only treatment for CABP is appropriate are eligible for enrollment.
- ^j Hematology and serum chemistry evaluations will be performed at each of the timepoints indicated. A serum or urine pregnancy test (for women only) and urine dipstick will be performed only at Screening. The relevant local laboratory results from Screening will be used to assess eligibility as per the inclusion/exclusion criteria.
- ^k Treatments that have been administered within the 7 days prior to the date of signing the ICF or during the Screening phase will be recorded in the eCRF. All medications and significant non-drug therapies administered after the first dose of test article must be recorded in the eCRF. Additional information, including start and stop time, will be collected for any prior or concomitant antibiotic.
- ¹ All oral doses should be taken in a fasted state (no food, antacids, or multivitamins containing multivalent cations [eg, aluminum, magnesium, calcium, bismuth, iron, or zinc] or drink except water for at least 6 hours before dosing). Subjects discharged with po test article will be asked to return all unused test article and packaging at each visit and site staff will perform accountability. The total duration of test article therapy for all subjects will be 7 to 10, up to 14 for bacteremia.
- ^m A full physical examination will be completed at Screening, thereafter only changes from Screening measurements should be recorded as AEs in the eCRFs.
- ⁿ Vital signs include body temperature, BP, pulse oximetry, pulse/heart rate, and RR.
- ^o BP and heart rate should be measured within 30 min before, and approximately (± 15 minutes) 1hour after the completion of the doses on Day 1.
- PK sample collection on Day 1:within an hour prior to Dose 1, 1, 1.5, 2, 2.5, 3, 4, 6, 8, 12 hours (12 hour taken immediately before Dose 2); Dose 2 administered (times relative to Dose 1); 13, 13.5, 14, 14.5, 15, 16, 24 hours post dose
- ^q PK sample collection on Day 2:within an hour prior to dose, 1, 1.5, 2, 2.5, 3, 4, 6 hours
- ^r PK sample collection on Day 3: prior to the Day 3 dose
- ^s PK sample collection on EOT is anytime during the visit after the final dose.

Stu	udy Ph	ase		Sci	eening	a	Treat	me	ent	Phase	Follo	DW-	up P	hase	;
							 		_				•		

^t The total duration of test article therapy for all subjects will be 7 to 10 days, up to 14 days for bacteremia.

^u A subject's AEs and SAEs will be recorded and reported from signing of the ICF to the Final Follow-up assessment.

